12.5. Electrocardiogram

The overall ECG interpretation will be summarized by presenting the number and percentage of subjects with “Normal”, “Abnormal, not clinically significant”, and “Abnormal, clinically significant”. Baseline and end of treatment (EOT) in the overall ECG interpretation will be displayed in cross-tabulations.

CCI

[Redacted]

[Redacted]

[Redacted]

[Redacted]

[Redacted]

[Redacted]

[Redacted]

[Redacted]

CC
[Redacted text block]

CELGENE PROPRIETARY INFORMATION

14. INTERIM ANALYSIS

14.1. General Information

The interim analysis on futility will support early assessment of efficacy and may minimize the number of subjects exposed to the investigational regimen in the absence of signs of efficacy.

An interim analysis for futility purposes following the completion of first stage will be conducted. The primary analysis will be conducted following the completion of second stage. The decision to proceed to Stage 2 after completion of Stage 1 will be performed independently in each cohort as mentioned below.

The DMC will review the safety data on a regular basis.

Myelodysplastic Cohort

An interim analysis for futility purpose will be conducted on the first 30 subjects who have completed 6 cycles of treatment unless they have established an earlier response (CR, mCR, PR or HI) or discontinued due to death or disease progression. Subjects assigned to Arm A, who received less than 3 cycles of durvalumab and continued under azacitidine monotherapy are to be excluded from the interim analysis.

The MDS cohort will be completed to include a total of 72 MDS subjects. Details of futility rules are given in [section 4.3.1](#).

Acute Myeloid Leukemia Cohort

An interim analysis for futility purpose will be conducted on the first 50 subjects who have completed 6 cycles of treatment unless they have established an earlier response (CR or CRi) or discontinued due to death or disease progression. Subjects assigned to Arm A, who received less than 3 cycles of durvalumab and continued under azacitidine monotherapy are to be excluded from the interim analysis.

The AML cohort will be completed to include a total of 110 AML subjects. Details of futility rules are given in [section 4.3.2](#).

Interim analyses for futility purposes are planned for each cohort as described above and will be based on the EE population.

14.2. Statistical Approaches for Control of Alpha

The interim analysis is for futility purposes, type I error will be well controlled.

15. CHANGES TO THE STATISTICAL ANALYSES SECTION OF THE PROTOCOL

Response derivations have been updated for consistency with IWG Response Criteria in Myelodysplasia (Cheson, 2006) and Modified IWG AML Response Criteria (Cheson, 2003).

IA requirements and definition of EE population have been detailed in order to specify that subjects assigned to Arm A, who received less than 3 cycles of durvalumab and continued under azacitidine monotherapy are to be excluded from interim analysis and/or in the EE population.

17. APPENDICES

17.1. Date Imputation Guideline

17.1.1. Impute Missing AE/Prior or Concomitant Medications Start Dates

If the stop date is nonmissing and the imputed start date is after the stop date, the start date will be imputed by the stop date.

Missing day and month

- If the year is **same** as the year of first day on study medication, then the day and month of the start date of study medication will be assigned to the missing fields
- If the year is **prior to** the year of first day on study medication, then December 31 will be assigned to the missing fields.
- If the year is **after** the year of first day on study medication, then January 1 will be assigned to the missing fields.

Missing day only

- If the month and year are **same** as the year and month of first day on study medication, then the start date of study medication will be assigned to the missing day.
- If the month and year are **before** the year and month of first day on study medication, then the last day of the month will be assigned to the missing day.
- If the month and year are **after** the year and month of first day on study medication, then the first day of the month will be assigned to the missing day.

Missing day, month, and year

- Included as TEAE

17.1.2. Impute Missing AE/ Prior or Concomitant Medications Stop Dates

If the imputed stop date is before the start date then the imputed stop date will be equal to the start date.

Missing day and month

- If the year of the incomplete stop date is the **same** as the year of the last dose date of study medication, then the day and month of the last dose date will be assigned to the missing fields.
- If the year of the incomplete stop date is **prior to** the year of the last dose date, then December 31 will be assigned to the missing fields.
- If the year of the incomplete stop date is **after** the year of the last dose date of study medication, then January 1 will be assigned to the missing fields.

Missing day only

- If the month and year of the incomplete stop date are the **same** as the month and year of the last dose date of study medication, then the day of the last dose date will be assigned to the missing day.
- If the month and year of the incomplete stop date are **before** the month and year of the last dose date of the study medication, then the last day of the month will be assigned to the missing day.
- If the month and year of the incomplete stop date are **after** the month and year of the last dose date of study medication, then the first day of the month will be assigned to the missing day.

17.1.3. Impute Missing Disease Diagnosis Dates

For partial diagnosis dates, January will be assigned to the missing month; and the first day of the month will be assigned to the missing day.

17.1.4. Impute Missing Dates in Prior Cancer Regimen

For each prior cancer regimen, the regimen start/stop date, disease progression date, best response date, and date of first response for PR or better, will be collected. If the day of any date is missing, then the first day the nonmissing month will be assigned to the missing day; if month or year of the date is missing, the date will not be imputed and treated as missing.

17.1.5. Impute Missing Dates in Subsequent Cancer Therapy

Subject will allow take other antimyeloma therapy after discontinued from the study. The cancer therapy start/stop date will be collected. If the day of any date is missing, then the last day the nonmissing month will be assigned to the missing day; if day and month are both missing, then the December 31 of the nonmissing year will be assigned to the missing day.

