The number and percentage of subjects who achieve each component of the overall response (CR, PR, mCR, HI-E, HI-P, HI-N) will be summarized together with associated two-sided 95% CI.

The best overall response per IWG 2006 response criteria will be summarized. The best overall response is defined as the best response prior to progressive disease and first subsequent therapy.

The below order will be considered for the definition of best response:

1. CR
2. PR
3. mCR
4. SD
5. PD
6. Disease transformation
7. Failure due to death
8. Not Evaluable/Missing

Acute Myeloid Leukemia Cohort

For the AML cohort, the primary efficacy endpoint is the proportion of subjects achieving an overall response rate (CR or CRi) based on modified IWG 2003 response criteria for AML ([Appendix 17.3](#)). The ORR will be summarized together with two-sided 95% CI. Subjects discontinued before 6-cycle treatment without achieving overall response will be counted as nonresponders.

The number and percentage of subjects who achieve CR, PR, CRi, HI-E, HI-P and HI-N will be summarized together with associated two-sided 95% CI

The best overall response per modified IWG response criteria will be summarized. The best overall response is defined as the best response prior to progressive disease and first subsequent therapy.

The below order will be considered for the definition of best response:

1. CR
2. CRi
3. CRc

4. PR
5. SD
6. PD
7. Treatment failure
8. Not Evaluable/Missing

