Progression-free survival is calculated as the time from randomization to the first documented progression, relapse or death due to any cause during or after the treatment period, whichever occurs first. Subjects who are still alive and progression-free will be censored at the date of their last response assessment. The PFS curve will be estimated using KM method.

Median PFS along with two-sided 95% CI will be provided for each cohort and treatment group. The PFS at 6 and 12 months will be estimated and compared using Kaplan-Meier (KM) method.

A sensitivity analysis of PFS will be performed, censoring PFS at the time of subsequent systemic anticancer therapy if the subject did not progress before that time.

Transformation to AML and Time to AML Transformation

Number of subjects with transformation to AML and time to transformation to AML will be summarized. Time to transformation to AML is defined as the time from the date of randomization until the date the subject has documented transformation to AML (at least 30% of BM blats). Subjects who do not transform to AML will be censored at the date last disease assessment date. Median time to transformation to AML and associated two-sided 95% CI will be estimated using KM method.

AML Cohort:

HI

Rate of HI – erythroid response (HI-E), hematological improvement – platelet response (HI-P) and hematological improvement – neutrophil response (HI-N) according to IWG 2006 response criteria for MDS ([Appendix 17.2](#)), will be provided together with Wald asymptotic two-sided 95% CIs.

Table 4: Event and Censoring Rules for Progression-free Survival, Duration of Response, Time-to-Response and Relapse-free Survival

Situation	Date of Progression or Censoring	Situation Outcome
Censoring Rules for PFS and DoR		
Progression	If the first PD is a scheduled assessment then Date of first PD; If the first PD is an unscheduled assessment and no previous assessment, then Date of PD; If the first PD is an unscheduled assessment and has previous assessment, then Date of previous assessment (regardless of the response type).	Event
Death between scheduled assessments or within the first two missed scheduled assessments	Date of death	Event
No progression	Date of last adequate assessment with evidence of no PD	Censored
Death or progression after two or more missed scheduled assessments	Date of last adequate assessment with evidence of no PD; if no adequate assessment exists then censored at date of first dose	Censored

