Censoring Rules for RFS		
Relapse	If the first relapse is a scheduled assessment then Date of first relapse; If the first relapse is an unscheduled assessment and no previous assessment, then Date of relapse; If the first relapse is an unscheduled assessment and has previous assessment, then Date of previous assessment (regardless of the response type).	Event
Death between scheduled assessments or within the first two missed scheduled assessments	Date of death	Event
No relapse	Date of last adequate assessment with evidence of no relapse	Censored
Death or progression after two or more missed scheduled assessments	Date of last adequate assessment with evidence of no relapse; if no adequate assessment exists then censored at date of first dose	Censored
Censoring Rules for PFS (sensitivity analysis), DoR and RFS		
Additional therapy received prior to progression or death	Date of additional systemic anticancer therapy	Censored

Censoring Rules for TTR		
Subject responded before PD	First documented response date (CR, PR, mCr, or HI for mDS Cohort, CR or CRi for AML Cohort)	Event
Subject responded after PD	Date of last adequate disease assessment at PD date or death date	Censored
Other case	Date of last adequate disease assessment; if no adequate assessment exists, then censored at date of first dose	Censored

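### Partial start dates of subsequent anticancer therapy are imputed to the latest possible day with no upper bound, which delays or removes censoring for DoR, RFS and the PFS sensitivity analysis

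*SAP*

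**What the plan says.** SAP Section 17.1.5 covers both ends of a later treatment: "The cancer therapy start/stop date will be collected". One instruction then applies to either date: "If the day of any date is missing, then the last day the nonmissing month will be assigned to the missing day", and "if day and month are both missing, then the December 31 of the nonmissing year will be assigned to the missing day". No limit follows. The section also refers to myeloma treatment, which is not a disease under study here.

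The start date is used in two places:

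- **Censoring (SAP Section 10.2, Table 4).** Under "Censoring Rules for PFS (sensitivity analysis), DoR and RFS", a subject who receives new therapy before progression or death is censored at "Date of additional systemic anticancer therapy". The PFS text describes the same sensitivity analysis: "censoring PFS at the time of subsequent systemic anticancer therapy if the subject did not progress before that time".
- **Best overall response (SAP Section 10.1, both cohorts).** "The best overall response is defined as the best response prior to progressive disease and first subsequent therapy".

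Neighbouring rules behave differently. Section 17.1.1 (adverse events and medications) contains a consistency check, beginning "If the stop date is nonmissing and the imputed start date is after the stop date", under which the start is pulled back to the stop date. For a year or month later than that of first dosing, it imputes 1 January or the first of the month. Section 17.1.4 (prior regimens) uses the first of the month and does not impute if the month is missing.

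**The concern.** Censoring at new therapy is meant to stop follow-up from counting once another drug may be responsible for the outcome. Moving an uncertain start date as late as the record allows works against that purpose. Late imputation is natural for a stop date, but here it also governs the start.

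Two things follow. First, time after the real start of new therapy stays in DoR, RFS and the PFS sensitivity analysis, and a death or progression in that stretch can count as an event where the plan intends a censoring. Second, nothing keeps the imputed start from falling after the therapy's own stop date, the subject's death or the data cut-off. The programmer must then improvise, in an open-label trial.

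Partial dates are plausible. After the safety visits, subsequent therapies are collected by telephone every 3 months (Protocol Sections 3.2.3.2 and 6.15).

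**Working it through.** The plan gives no figure for this rule, so there is none to reproduce. The check is calendar arithmetic on the rule as written, followed by a trace of the endpoints it reaches.

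**1. Size of the date error.** Delay = imputed date minus true date. Assumption: true dates are uniform over the unknown part.

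- Day missing: 0 to 30 days. For a month of n days the delays sum to n(n−1)/2. Over a 365-day year that is (7×465 + 4×435 + 378)/365 = 5373/365 = 14.7 days on average.
- Day and month missing: 0 to 364 days, mean 182 (maximum 365 and mean 182.5 in a leap year).

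The delay is never negative.

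**2. Passing death or cut-off.** For a year-only date, the imputed start falls after an event k days after the true start when the delay exceeds k, with probability (364−k)/365:

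- k = 90: 274/365 = 75%
- k = 180: 184/365 = 50%
- k = 270: 94/365 = 26%

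With only the day missing, this happens only if the event falls later in the same month.

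**3. One illustrative subject (all dates assumed).** Response 1 Sep 2017; last dose 10 Feb 2018; discontinuation assessment 17 Feb 2018; new therapy 5 Mar 2018; death 20 Jul 2018; cut-off 31 Oct 2018; no relapse or progression. DoR in months is the inclusive day count divided by 30.4375 (the conversion in SAP Section 5.1.2).

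- True date: censored at 186/30.4375 = 6.1 months.
- Month and year known: imputed 31 Mar 2018, 26 days late; censored at 212/30.4375 = 7.0 months.
- Year only: imputed 31 Dec 2018, 301 days late, after both death and cut-off. Read literally, Table 4's therapy row no longer applies because the imputed start does not precede death, so death becomes an event at 323/30.4375 = 10.6 months. A program that censors at the imputed date regardless gives 487/30.4375 = 16.0 months, later than both death and cut-off.

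The same rule thus lengthens follow-up in one reading and adds an event in the other.

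**4. What limits the effect.** Table 4 censors a death or progression after two or more missed scheduled assessments at the last adequate assessment. Assessments come every third 28-day cycle, so if that grid is taken to continue after discontinuation (the SAP does not say), the limit is 2 × 84 = 168 days. In the example, death comes 153 days after the last assessment and still counts; after 168 days it would not. Table 4 also sends a subject without progression to the last adequate assessment and states no order of precedence between that row and the therapy row.

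**5. Upper bound on misclassified events.** Assume the median time from new therapy to progression or death is 4 to 10 months. The chance of an event inside the gap is the average of 1 − exp(−ln 2 × gap/median) over the uniform gap. It is 32% (median 10) to 58% (median 4) for a year-only date, and 3% to 8% with only the day missing. These are per affected subject and ignore step 4.

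**The case against.** The strongest opposing case is that the rule hardly matters.

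- **Responses.** A reader might infer that responses to the next drug are credited to study treatment. The documents do not support that. CR, PR, marrow CR and CRi all need a marrow. The Table of Events (Protocol Section 5) schedules neither marrow nor IWG assessment after the treatment discontinuation visit. Other anticancer drugs are prohibited during the study (Protocol Section 8.2). Haematological improvement is not in the SAP's ranking for best overall response. This objection stands.
- **Direction.** A reader might also infer that the error always flatters response duration. Only the date moves one way. Extra event-free time raises a Kaplan-Meier curve, while a censoring turned into an event lowers it. The rule is the same in both arms, and nothing in the documents shows a differential effect. This stands too.
- **Size.** The affected group needs a partial date and new therapy before progression or relapse; DoR and RFS also need a prior response. Repeated contacts, edit checks and source verification should make year-only dates rare. This stands, and the 32% to 58% range cannot be read as a rate in the trial.
- **The remedy.** Earliest-date imputation could reverse the error. A floor at the day after last dose is too early: azacitidine ends on Day 7 and the marrow is taken around Day 22, so a genuine response or progression at end of treatment could fall after the imputed start. This is right and shapes the fix.

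None of this supplies the missing bound or explains why a start date should follow the stop-date rule.

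**Conclusion.** The point holds as a minor one. As written, the imputed start is never early and can pass the therapy's stop date, death or cut-off. That delays or removes censoring at new therapy in DoR, RFS and the PFS sensitivity analysis. The mean delays of about 15 and 182 days assume uniform true dates.

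The reach is narrow. OS and main PFS are not censored at new therapy, the primary ORR test as written does not use this date, and best overall response is barely touched. The documents do not give the number of partial dates, so the bias in any estimate cannot be computed, and its sign is not fixed.

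**What to change.** Replace the single rule in SAP Section 17.1.5 with two:

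- **Start date:** the earliest date consistent with the recorded parts, but, where those parts allow, not before the later of the day after last study dose and the treatment discontinuation disease assessment. Treat an assessment on the imputed day as preceding the new therapy. Never impute later than a known therapy stop date, death, last contact or data cut-off.
- **Stop date:** keep late imputation, capped at death, last contact or data cut-off.

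Report the number of imputed dates by arm and by type (day missing, or day and month missing).

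For the illustrative subject, a year-only start becomes 17 Feb 2018, 16 days early (170/30.4375 = 5.6 months, against a true 6.1). A month-and-year start becomes 1 Mar 2018, 4 days early (182/30.4375 = 6.0 months).

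The cost is one rewritten rule and no new data. The downside is somewhat earlier censoring. If last dose and the discontinuation assessment fell in the previous calendar year, a year-only date goes to 1 January and could be up to 364 days early, which is why the count should be shown. Early censoring discards some follow-up but does not count time on another drug, which suits the purpose of these analyses better.

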17.2. International Working Group (IWG) Response Criteria in Myelodysplasia (Cheson, 2006)

Altering Disease Natural History	
Complete remission (CR)	
 ▪ BM Blasts \leq 5% 
AND
 
 ▪ All of the following peripheral blood values met: 
 ▪ Hemoglobin \geq 11 g/dL ▪ Platelets \geq 100 x10⁹/L ▪ ANC \geq 1.0 x10⁹/L ▪ Peripheral Blasts=0% 
Labs must meet criterion for at least 28 consecutive days. If not confirmed for 28 days then response should be mCR.
 
In addition
 
 ▪ The 7/3 rule should be applied to Hemoglobin. ▪ Platelets collected 3 days period following Platelet transfusion will not be used - ANC values that must be at least 14 days following a G-CSF application
Partial remission (PR)	
 ▪ BM Blasts decreased by \geq 50% over pretreatment but still $>$ 5% 
AND
 
 ▪ All of the following peripheral blood values met: 
 ▪ Hemoglobin \geq 11 g/dL ▪ Platelets \geq 100 x10⁹/L ▪ ANC \geq 1.0 x10⁹/L ▪ Peripheral Blasts=0% 
Labs Must meet criterion for at least 28 consecutive days.
 
In addition
 
 ▪ The 7/3 rule should be applied to Hemoglobin. ▪ Platelets collected 3 days period following Platelet transfusion will not be used 
ANC values that must be at least 14 days following a G-CSF application

Marrow CR	
 ▪ Bone marrow: $\leq 5\%$ myeloblasts and decrease by $\geq 50\%$ over pretreatment with baseline BM blast $>5\%$ 
AND
 
 ▪ Not all of the following peripheral blood values met or none are met: 
 ▪ Hemoglobin ≥ 11 g/dL ▪ Platelets $\geq 100 \times 10^9/L$ ▪ ANC $\geq 1.0 \times 10^9/L$ ▪ Peripheral Blasts=0% 
Peripheral blood: if HI responses, they will be noted in addition to marrow CR

Stable disease (SD)	Any evaluable time point where criteria for all other response categories (i.e., CR, PR, PD, Failure due to death, Not Assessable) are not met
Failure	Death during treatment
Disease Progression (PD)	
 ▪ If condition for Transformation to AML and relapse after CR/PR are not verified ▪ For patients with: 
 ▪ Nadir value less than 5% blasts: $\geq 50\%$ increase in blasts to $> 5\%$ blasts ▪ Nadir value 5% - 10% blasts: $\geq 50\%$ increase in blasts to $> 10\%$ blasts ▪ Nadir value 10% - 20% blasts: $\geq 50\%$ increase in blasts to $> 20\%$ blasts 
AND ANY OF THE FOLLOWING
 
 ▪ $\geq 50\%$ decrement from max level of ANC and ANC < 1.0 GI/L 
OR
 
 ▪ $\geq 50\%$ decrement from max level of Platelets and Platelets < 100 GI/L 
OR
 
 ▪ Reduction from max level of Hgb ≥ 20 g/L and Hgb < 110 g/L 
OR
 
 • Transfusion dependence (apply to baseline TI subjects only)

^a Dysplastic changes should consider the normal range of dysplastic changes (modification).

Source: Cheson BD, Greenberg PL, Bennett JM, Lowenberg B, Wijermans PW, Nimer SD, et al. Clinical application and proposal for modification of the International Working Group (IWG) response criteria in myelodysplasia. Blood. 2006; 108(2): 419-25.

Altering Disease Natural History	
Disease transformation	Transformation to AML (30% or more blasts)
Relapse after CR or PR	
 • BM % blast \geq baseline % blast and BM % blast \geq 5% 
OR
 
 • \geq 50% decrement from max level of ANC and ANC < 1.0 GI/L 
OR
 
 • \geq 50% decrement from max level of Platelets and Platelets < 100 GI/L 
OR
 
 • Reduction from max level of Hgb \geq 20 g/L and Hgb < 110 g/L 
OR
 
 • RBC/platelet transfusion is given after CR/PR

Cytogenetic Response	
Complete	Disappearance of the chromosomal abnormality without appearance of new ones
Partial	At least 50% reduction of the chromosomal abnormality

Hematological Improvement (HI)	
Erythroid response (HI-E) (Pretreatment < 11 g/dL)	
 ▪ Hgb increase by \geq 1.5 g/dL in \geq 8 weeks 
OR
 
 ▪ Relevant reduction of units of RBC transfusions by an absolute number of at least 4 RBC transfusions/8 weeks compared with the pretreatment transfusion number in the previous 8 weeks. Only RBC transfusions given for a Hgb of \leq 9.0 g/dL pretreatment will count in the RBC transfusion evaluation 
 ▪ For Hgb, 7/3 rule should be applied first
Platelet response (HI-P) (Pretreatment < $100 \times 10^9/L$)	
 ▪ in \geq 8 weeks Absolute increase of $\geq 30 \times 10^9/L$ for patients starting with $> 20 \times 10^9/L$ 
OR
 
 ▪ Increase from $\leq 20 \times 10^9/L$ to $> 20 \times 10^9/L$ and by at least 100%

Neutrophil response (HI-N) (Pretreatment $< 1.0 \times 10^9/L$)	
 ▪ in ≥ 8 weeks At least 100% increase and an absolute increase from mean of pre-dose of $> 0.5 \times 10^9/L$
---	---

AML = acute myeloid leukemia; Hgb = hemoglobin; RBC = red blood cell

Source: Cheson BD, Greenberg PL, Bennett JM, Löwenberg B, Wijermans PW, Nimer SD, et al. Clinical application and proposal for modification of the International Working Group (IWG) response criteria in myelodysplasia. Blood. 2006; 108(2): 419-25.

